6.3 Presenting clinical characteristics and routine tests

For all characteristics (candidate predictors) we will present the odds ratio, p-value and 95% confidence interval (CI) from a univariable analysis. For binary characteristics we will also present the distribution of adverse outcomes in each category. If a continuous characteristic has pre-specified cut-off points the distribution of adverse outcomes will be presented for each category.

The following clinical characteristics and routine tests will be evaluated.

Continuous Characteristic	Cut offs	Adults	Children	Initial assessment model	Full model
Age	None	\checkmark	\checkmark	\checkmark	\checkmark

Symptom duration		✓	~	✓	✓
Number of current		1	1	√	√
medications		·		·	·
Urea		√	✓		✓
Creatinine		√	~		✓
Respiratory rate	0= 12-20 or missing 1= 9-11	1			
	2= 21-24 3= <9 or >24	·	v	· ·	· ·
Pulse rate	0= 51-90 or missing 1= 41-50 or				
	91-100 2= 111-130 3= <41 or	\checkmark	~	~	\checkmark
	>130				
Temperature	0= 36.1-38.0 or missing 1= 35.1-				
	36.0 or 38.1-39.0 2= >39.0 3=	✓	✓	~	✓
	<35.1				
Systolic Blood	0= 111-219 or missing 1=101-				/
Pressure	110 2= 91-100 3= <91 or >219	v	v	v	v
SaO ₂	0= >95 or missing 1= 94-95 2=				
	92-93 3= <93 (add two points	✓	✓	✓	\checkmark
	for FiO ₂ >21%)				
SaO ₂ /FiO ₂ ratio		✓	✓	√	✓
GCS Total ^a	1= Severe (<8) 2= Moderate (9-				/
	12) 3= Mild (13-15)	v	v	v	v
Na	1= Low (<136) 2=Normal (136-				
	142) 3 = High (>142)	v	v		v
К	1= Low (<3.5) 2=Normal (3.5-				
	5.0) 3 = High (>5.0)	v	v		v
Hb	1= Low (<130 males, <115				
	females) 2=Normal (130-180				/
	males, 115-165 females) 3 =	v	v		v
	High (>180 males, 165 females)				
Platelets	1= Low (<150) 2=Normal (150-				/
	400) 3 = High (>400)	v	v		v
WCC	1= Low (<4) 2=Normal (4-11) 3	1	1		
	= High (>11)	V	V		V
Neutrophils	1= Low (<2.0) 2=Normal (2.0-				
	7.5) 3 = High (>7.5)	V	V		V
Lymphocytes	1= Low (<1.5) 2=Normal (1.5-				
	4.5) 3 = High (>4.5)	~	×		√
Lactate		✓	✓		~

C-Reactive	~	~	~
D-dimer	~	~	~
Troponin	~	~	~

a) Both GCE and AVPU will be analysed in univariable analysis, however in multivariable analysis AVPU will be used and missing AVPU data will be imputed using GCE scores (see section 7.1.2 for the imputation rules).

Binary				Initial	
Characteristic	Levels	Adults	Children	assessment	Full model
enaracteristic				model	
Sex	Male/Female	~	~	~	\checkmark
Presenting features	Presence/Absence per feature				
(Shortness of breath,					
cough, fever, sore					
throat, headache,		1	1	 	1

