6.4.1 Converting the predictive model into a triage tool

Integer weights will be assigned to each category of predictor variable according to the coefficient derived from a multivariable model using categorised continuous predictors. This will generate a composite clinical score in which risk of adverse outcome increases with the total score.

Clinical members of the PMG will review the multivariable prediction models and provide input into the derivation of the triage tools. They will input into the following:

- Reviewing the multivariable prediction model for
 - o Clinical credibility of predictors included in the model
 - o Clinical credibility of the direction and magnitude of effect of predictors in the model
- Deciding whether coefficients can be rounded to integer values
- Deciding if using cut-offs for continuous variables are appropriate and choosing the number and placement of cut-offs (it is expected existing cut-offs will be used as specified in section 6.3 as 'optimal' cut offs found in the models may not translate to other cohorts)
- Reviewing the number of predictors included in the prediction model and deciding if these need to be reduced for ease of use in the emergency department setting (initial discussion in the PMG suggested 8 factors as an upper limit).

A threshold for decision making will be decided upon based on clinical review but will include the following

• A cut-off that ensures sensitivity exceeds 95%

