8.5 NEWS2

The NEWS2 has seven parameters which are scores from zero to three providing an overall score between zero and 20. The scores for each parameter can be found in the table below.

Score	3	2	1	0	1	2	3
Respiratory Rate	≤8		9-11	12-20		21-24	≥25
SaO₂	≤91	92-93	94-95	≥96			
Pulse Rate	≤40		41-50	51-90	91-110	111-130	≥131
Systolic BP	≤90	91-100	101-110	111-219			≥220
Temperature	≤35.0		35.1-36.0	36.1-38.0	38.1-39.0	≥39.1	
Neuro				Alert			Confusion, Voice, Pain, Unresponsive
Air or Oxygen		Oxygen (based on FiO ₂ >21%, or FiO ₂ >0 L/min)		Air			

Missing data: Any missing data will be imputed with the value zero, therefore classifying missing as normal. Low rates of missing data are expected for the physiological parameters. Sensitivity analysis will be considered if physiological variables have missing rates > 5%. The score will not be calculated if fewer than three of the parameters are available. The scale for patients with confirmed hypercapnic respiratory failure will not be used. For ROC analysis the raw score outlined above will be used. To calculate sensitivity and specificity at key cut-offs high risk will be defined as scoring at least 5, or scoring 3 points in any one of the above categories.

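### Section 6.3 gives pulse 101-110 no category and puts SaO2 92% in two, contradicting the SAP's own NEWS2 table, so the categorised analyses cannot be coded unambiguously

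*SAP*

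**What the plan says.** The table of continuous characteristics in SAP section 6.3 pre-specifies these cut-offs:

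- **Pulse.** The entry opens "0= 51-90 or missing 1= 41-50 or" and continues "91-100 2= 111-130 3= <41 or", with above 130 completing category 3.
- **SaO2.** Category 0 is above 95 or missing and category 1 is 94-95. Categories 2 and 3 read "92-93 3= <93 (add two points", the added points being for an FiO2 above 21%.
- **GCS total.** The entry begins "1= Severe (<8) 2= Moderate (9"; the moderate band runs to 12 and the mild band is 13-15.

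The NEWS2 table in section 8.5 scores pulse on the normal and high side as "51-90 91-110 111-130" (0, 1 and 2 points) and SaO2 as "≤91 92-93 94-95 ≥96" (3, 2, 1 and 0 points).

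The 6.3 categories are used in three places:

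- Section 6.3 requires the distribution of adverse outcomes by category wherever cut-offs are pre-specified.
- Section 7.1 includes a scenario in which missing values of categorised predictors are taken as normal, and Appendix 1 refers to 6.3 for that coding.
- Section 6.4.1, on converting the model into a triage tool, takes integer weights from the "coefficient derived from a multivariable model using categorised continuous predictors" and adds that "it is expected existing cut-offs will be used as specified in section 6.3".

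**The concern.** A categorisation has to place every recordable value in exactly one category. The pulse and SaO2 bands in 6.3 do not, so the analyst must make a choice that the plan has not made, with outcome data already in hand.

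Pulse is the more serious case. Its reference category also collects missing values, so a recorded pulse of 101-110 that matches no rule could be handled as though it had not been measured, or as though it were normal. It would then sit below a pulse of 95, which is in category 1. For SaO2 92%, the order of the code lines could decide the category. Both variables are candidates for the initial assessment model and the full model, so the definitions can reach the new triage tools that objective 4 sets out to develop.

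**Working it through.** There is no sample-size or power figure to reproduce. The check is whether each possible value meets exactly one of the written conditions.

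**Step 1: run the 6.3 bands value by value.**

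| Variable (range checked) | In no category | In two categories |
|---|---|---|
| Pulse (0-250) | 101 to 110, ten values | none |
| SaO2 (50-100%) | none | 92, in 2 and 3 |
| GCS (3-15) | 8 | none |
| Respiratory rate (0-70) | none | none |
| Systolic BP (30-299) | none | none |
| Temperature (30.0-42.9, in steps of 0.1) | none | none |

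**Step 2: run the 8.5 bands the same way.** Pulse and SaO2 in the NEWS2 table have no gap and no overlap.

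**Step 3: set the two sections side by side.**

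| Variable | 6.3 | 8.5 |
|---|---|---|
| Respiratory rate, category 3 | <9 or >24 | ≤8 or ≥25 (same) |
| Systolic BP, category 3 | <91 or >219 | ≤90 or ≥220 (same) |
| Temperature, categories 3 and 2 | <35.1; >39.0 | ≤35.0; ≥39.1 (same to 0.1 degree) |
| Pulse, category 1, high side | 91-100 | 91-110 (differs) |
| SaO2, category 3 | <93 | ≤91 (differs) |

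The remaining bands for these five variables agree. The only two departures from 8.5 are the ones that create the gap and the overlap. The SaO2 row in 6.3 also carries the two points for oxygen that 8.5 scores separately. The 6.3 bands therefore appear to be meant as the NEWS2 bands, with two slips.

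**Step 4: follow an unmatched pulse.** Suppose the code leaves 105 unassigned in the categorised variable. The consequence then depends on the scenario in 7.1. Under missing-as-normal it becomes category 0. If missing is left as missing, the value is lost. Under multiple imputation, if the category itself is imputed, a measured value is replaced by an imputed one. None of this follows if the code handles 101-110 explicitly, but the plan does not say how it should.

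**Step 5: size of the gap.** The SAP gives no pulse distribution, so this is an assumption. For a normal pulse with mean m and SD s, the share is Φ((110.5 − m)/s) − Φ((100.5 − m)/s).

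| Mean | SD 15 | SD 20 | SD 25 |
|---|---|---|---|
| 80 | 6.5% | 8.9% | 9.5% |
| 85 | 10.6% | 11.8% | 11.4% |
| 90 | 15.6% | 14.7% | 13.1% |
| 95 | 20.6% | 17.2% | 14.5% |
| 100 | 24.5% | 19.0% | 15.5% |
| 105 | 26.1% | 19.7% | 15.8% |

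The range is about 6% to 26%.

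**Step 6: the proposed bands.** With pulse category 1 as 41-50 or 91-110 and SaO2 category 3 as <92, the bounds equal those in 8.5 for whole-number values, so every value falls in exactly one category.

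**The case against.** The best case on the other side is that these are slips whose complete counterparts stand in the same document, and that their reach is limited. Section 6.4 enters continuous predictors as continuous first and only investigates cut-offs. Section 6.4.1 lets clinical members of the PMG decide whether cut-offs are appropriate and choose their number and placement. Unassigned values should also show up when category counts are tabulated. All of this stands, and it makes the effect on the triage score conditional. It does not rescue the outcome-by-category tables, which 6.3 requires regardless, and 6.3 remains the stated default for the score.

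A reader might infer more than the SAP supports, in four ways:

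- **That GCS 8 will be mis-scored in the model.** Footnote a in 6.3 uses AVPU in place of GCS in multivariable analysis, so the gap affects only the univariable presentation. The GCS boundary that can reach the models is a separate one: 7.1.2 maps GCS 9 to both V and P.
- **That the weights will be biased and non-monotone.** For pulse this is a risk only if code lets unmatched values into category 0; a recorded 105 is neither 51-90 nor missing. For SaO2 it is not shown: 92% is ambiguous between two adjacent categories, and the weight is estimated from whoever is placed there.
- **That SaO2 92% moves between 2 and 3 points in the new score.** The 6.3 numbers are category codes. The new score's points come from model coefficients and are not yet known.
- **That a number of affected patients can be stated.** The planned 20,000 includes children, and the SAP gives no pulse distribution for either age group.

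**Conclusion.** The point holds as a defect of definition. Section 6.3 has no category for pulse 101-110 and two for SaO2 92%, and in both it contradicts section 8.5. The analyses that cannot be coded unambiguously are the outcome-by-category tables, the missing-as-normal scenario for the categorised variables, and the categorised model behind the integer score if the 6.3 cut-offs are kept. The pulse gap covers about 6-26% of patients, on the assumption of a roughly normal pulse with mean 80-105 and SD 15-25. The SaO2 overlap is a single value, and its frequency is not given. GCS 8 is a minor gap in the univariable presentation. The models with continuous predictors and the evaluation of the existing NEWS2, which uses 8.5, are unaffected. The bands should be settled before any categorised analysis is run, because repairing them afterwards would be an unplanned choice made with outcomes visible.

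**What to change.** Before any categorised analysis:

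1. In 6.3, set pulse category 1 to 41-50 or 91-110 and SaO2 category 3 to <92, so that both agree with 8.5. If a departure from 8.5 was intended, state it and give bands without gap or overlap.
2. Make the GCS bands exhaustive by assigning 8 to one of the two neighbouring bands. The SAP does not indicate which.
3. Add a programmed check that every observed value falls in exactly one category and that only truly missing values receive the missing code.

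The cost is three table entries and the matching code. No new data are needed, and the sample size does not change.

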The potential predictors considered for the predictive model will be those listed in section 6.3; whether the predictor will be considered for the initial assessment model or the full model is given in each table. The sample size calculation specified that at least 20 potential prediction factors could be assessed in a multivariable model but as many as 30 or more could be considered depending on the number of cases and adverse outcome events. Before estimating the relationship between predictors and outcome in a prognostic model, the potential to collapse correlated predictors, or keep one of a set of correlated predictors will be investigated (see section 6.4.1). All continuous predictors will be included as continuous in prediction models in the first instance but the use of cut-offs will be investigated. The potential cut-points to base categorisation of continuous predictors are listed in section 6.3. Non linear prognostic effects for continuous predictors will also be investigated (see section 7.2). Any predictor with more than 50% missing data will not be considered for inclusion in the predictive model. The initial assessment prognostic model will be built first, all prognostic factors that remain in that model after model building will be included with the bloods and tests to be considered for inclusion for the full model.

The stability of derived models will be assessed using bootstrap methods with visual calibration methods (section 7.3) [16] [17].

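### Section 6.3 adds two to the SaO2 category code for oxygen, so two of the six codes mix patients on oxygen with more hypoxic patients on air, and the categorised score has no separate oxygen item

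*SAP*

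**What the plan says.** **Section 6.3 (candidate predictors).** SaO2 is ticked for adults, children, the initial assessment model and the full model. Code 0 is above 95 or missing, and code 1 is 94-95. The row then continues "92-93 3= <93 (add two points", the addition applying when FiO2 is above 21%. The next row is the SaO2/FiO2 ratio, with the same ticks and no cut-offs. None of the three predictor tables has a row for breathing air or oxygen. The section also promises the distribution of adverse outcomes in each category of a predictor with pre-specified cut-offs.

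**Section 6.4 (model development).** "The potential predictors considered for the predictive model will be those listed in section 6.3". On functional form: "All continuous predictors will be included as continuous in prediction models in the first instance but the use of cut-offs will be investigated". On the source of the cut-offs: "The potential cut-points to base categorisation of continuous predictors are listed in section 6.3".

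**Section 6.4.1 (conversion to a triage tool).** On how the weights are set: "Integer weights will be assigned to each category of predictor variable according to the coefficient derived from a multivariable model using categorised continuous predictors". Clinical members of the Project Management Group (PMG) decide whether cut-offs are appropriate, how many, and where, but "it is expected existing cut-offs will be used as specified in section 6.3".

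**Section 8.5 (NEWS2).** "The NEWS2 has seven parameters which are scores from zero to three providing an overall score between zero and 20". Oxygen has its own row there, worth 2 points, separate from the saturation row.

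**The concern.** In NEWS2 the output is a fixed sum, so points for saturation and points for oxygen can simply be added. In section 6.3 the numbers 0 to 3 label categories whose weights are still to be estimated. Adding two to a label moves a patient into a category that may already hold other patients. Someone saturating well on oxygen is then recorded in the same way as someone with low saturation on air.

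Two outputs are affected. The first is the integer score, where both groups in a shared code receive the same weight and no other item records oxygen use. The second is the descriptive summary of adverse outcomes by SaO2 category, where a reader could not tell what the middle categories contain. Whether oxygen use and low saturation on air carry similar risk is a question the derivation should answer from the data.

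**Working it through.** **1. The plan's own figure.** The section 8.5 range can be reproduced only with oxygen as a separate item: six parameters with a maximum of 3, plus oxygen with a maximum of 2, gives 6 × 3 + 2 = 20. This matches the stated maximum.

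**2. Codes under the section 6.3 rule.** Code = saturation band (0 to 3) + 2 if FiO2 > 21%.

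| Code | On air | On oxygen |
|---|---|---|
| 0 | >95 | none |
| 1 | 94-95 | none |
| 2 | 92-93 | >95 |
| 3 | lowest band | 94-95 |
| 4 | none | 92-93 |
| 5 | none | lowest band |

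Air gives {0, 1, 2, 3} and oxygen gives {2, 3, 4, 5}. The 4 × 2 = 8 states become 6 codes, and codes 2 and 3 are mixed. Codes 4 and 5 contain only patients on oxygen, but the row does not define them.

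**3. Can oxygen be recovered from the codes?** A matrix-rank check on the eight states shows that the oxygen indicator is not a linear combination of the six code indicators. Neither is any of the four saturation bands. So neither saturation nor oxygen has a weight of its own in the categorised coding.

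**4. What the SaO2/FiO2 ratio adds.** The FiO2 values on oxygen are assumptions.
- Code 2: 92-93 on air gives 92/0.21 = 438 to 93/0.21 = 443. Saturation 96-100 at FiO2 24% gives 96/0.24 = 400 to 100/0.24 = 417. At 23% the maximum is 100/0.23 = 435. The ratio separates these two groups.
- Code 3: 94-95 at FiO2 24% gives 94/0.24 = 392 to 95/0.24 = 396. A saturation of 83 on air gives 83/0.21 = 395. Here the ratio can coincide for the two groups.
- With simulated values (saturation uniform over 82-100, 30% on oxygen, FiO2 of 24, 28, 35, 40 or 60%), the six codes account for 69% of the variance of the oxygen indicator, and 82% with the ratio added. The information is partial under these assumptions.

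**5. Parameters, excluding the intercept.** Six codes need 6 − 1 = 5. Four bands plus oxygen yes/no need (4 − 1) + 1 = 4. All eight states would need 8 − 1 = 7.

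**6. A second defect in the same cell.** Code 2 is 92-93 and code 3 is below 93, so a value of 92 meets both definitions. Section 8.5 gives 3 points at 91 or below. The two sections need to be reconciled.

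**The case against.** The strongest defence is that the coding is provisional and that oxygen enters the models by another route. Continuous predictors are fitted as continuous first, so the initial models use raw SaO2 and the ratio and have no collision. The section 6.3 values are only potential cut-points, and the PMG may change them. The ratio is a candidate in both models and, as shown above, can distinguish the patients merged in code 2.

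Most of this stands, and it rules out several stronger readings that a reader might infer.
- *That the models cannot learn anything about oxygen.* The ratio carries oxygen information, so a regression holding both predictors need not give the merged groups the same risk.
- *That the NEWS2 weight of two points is imposed on the new score.* With a freely estimated coefficient per code, the constraint is only equality within two pairs of states. A fixed oxygen effect of two saturation steps would follow only if the code were entered as a linear score, and section 6.4.1 describes weights per category.
- *That discrimination and calibration must suffer.* Separate bands plus oxygen assume one constant oxygen effect, which the merged codes do not. Neither model is nested in the other, so neither must perform better. The SAP gives no risks by saturation and oxygen status from which to calculate a loss.
- *That patients on oxygen with missing SaO2 are routinely given code 2.* For model building, this arises only where missing is treated as normal, which is a comparison scenario. Section 7.1 makes multiple imputation primary.

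The defence does not remove the point for the score. That tool is built from categorised predictors, its expected cut-offs are those of section 6.3, the ratio has none listed, and moving cut-offs does not add an oxygen candidate to the list.

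**Conclusion.** The concern holds for the categorised SaO2 predictor. Followed as written, section 6.3 produces six codes, two of which combine patients on oxygen with more hypoxic patients on air. If section 6.4.1 uses the section 6.3 cut-offs as expected, each mixed group shares one integer weight and the categorised score has no separate oxygen item. The summary of adverse outcomes by SaO2 category is mixed in the same way.

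The collision follows from the coding alone and needs no assumption about risk. The effect on the score assumes that the PMG keeps the listed cut-offs. The effect on performance is unknown: it depends on how far risk differs within codes 2 and 3, how many patients fall there, and whether the ratio is retained and categorised. The continuous models are not affected by the collision. The SAP wording should be corrected before the categorised model is fitted.

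**What to change.** In section 6.3:
- Delete from the SaO2 row the parenthesis that raises the code by two for FiO2 above 21%.
- Add supplemental oxygen (yes/no) to the binary predictors, ticked for both the initial assessment model and the full model.
- Reconcile the two SaO2 bands that overlap at 92 with the bands in section 8.5.

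Keep the two-point addition only in the NEWS2 scoring in section 8.5. In section 6.4.1 on correlation between prediction factors, state how the oxygen term and the SaO2/FiO2 ratio are handled under the rule that only one of a set of highly correlated factors is chosen.

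The cost is a small SAP edit. FiO2 is already needed for the ratio and for NEWS2, so no new data are required. The categorised coding falls from 5 parameters to 4. The downside is one more binary candidate that is correlated with the ratio.

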7.1.2 Missing AVPU

For the multivariable analysis models AVPU will be used and GCS Total will be used to impute AVPU score where AVPU is not available. The following rules will be used:

- GCS 15 = A,
- GCS 9-14 = V,
- GCS 7-9 = P,
- GCS 3-6 = U.

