8.3 PMEWS

PMEWS uses six physiological parameters and patient parameters to calculate a score from zero to 19. The score is calculated by taking the score in the table below dependent on each of the six physiological parameters then adding points for two patient parameters after if they are positive.

Physiological:

Score	3	2	1	0	1	2	3
Respiratory Rate	≤8			9-18	19-25	26-29	≥30
SaO ₂	<89	90-93	94-96	>96			
Pulse Rate	≤40	41-50		51-100	101-110	111-129	≥130
Systolic BP	≤70	71-90	90-100	>100			
Temperature		≤35.0	35.1-36.0	36.1-37.9	38-38.9	≥39	
Neuro				Alert	Confused Agitated*	Voice	Pain Uncon

* confused/agitated will be defined based on GCS-V<4 or GCS total<15, or if confusion is ticked as a presenting feature

Patient:

- 1. Add 1 point if age>65
- 2. Add 1 point if either:
 - a. Patient lives alone / no fixed abode or
 - b. has a co-morbidity (respiratory, cardiac, renal, immunosuppressed, diabetes)
 - c. performance status is more than two suggesting limited activity can self-care, limited activity limited self-care, or bed/chair bound no self-care.

Missing data: If data is missing one or two variables then the normal score (zero) should be assumed. If more than three variables are missing the patient should be excluded. These rules effectively classify

missing data as normal. Low rates of missing data are expected for the physiological parameters and age. The remaining parameters only account for one point and therefore would be within the range of using the patient data. Sensitivity analysis will be considered if physiological variables have missing rates > 5%. If AVPU is missing and GCS is recorded, impute the following AVPU scores using GCS: 0 if GCS=15, 1 if GCS=12-14; 2 if GCS=9-11 and 3 if GCS<9.

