8.6.1 WHO algorithm in children

The WHO decision-making algorithm for hospitalisation with pneumonia suggests a child is admitted (score 1) if any of the following are present:

- respiratory rate: >30/minute if over 5 years old; \ge 40/min if 1-5 years old; or \ge 50/min if <1year old
- oxygen saturation <90%
- respiratory distress, respiratory exhaustion or severe dehydration ticked
- AVPU is P or U, or GCS<13
- any of the following comorbidities are present; diabetes, cardiovascular disease, chronic respiratory disease, renal impairment, immunosuppression

A patient will score 0 otherwise. Any missing data will be assumed as normal. A score will not be calculated if fewer than three of the above are complete.

8.7 **POPS**

Paediatric Observation Priority Score (POPS) will be calculated for the child cohort only. The scoring chart is given below:

Paediatric Observation Priority Score (POPS) Chart

This chart is not a substitute for good clinical judgement and any concerns about the condition of a child should be brought to the attention of a senior nurse or doctor

Age	Score	2	1	0	1	2	Total	
Any	Sats	<90%	90-94%	>95%	90-94%	<90%	Score	Priority
Any	Breathing	Stridor	Audible grunt or wheeze	No distress	Mild or Moderate Recession	Severe Recession	0-1	
Any	AVPU	Pain	Voice	Alert	Voice	Pain		
Any	Gut Feeling	High level concern	Low level concern	Well	Low level concern	Child looks unwell	2-3	
Any	Other	Oncology Patient	Significant PMH*		Significant PMH*	Congenital heart disease	4-7	Immediate
							0.	review
	Pulse	<90	90 - 109	110 - 160	161 - 180	180+		
0-1	RR	<25	25 - 29	30 - 40	41 - 50	50+	Any c	hild scoring
	Temp	<35°	35 – 35.9°	36 - 37.5°	37.6 - 39°	39°+	abov	e 8 should
							he cor	sidered for
	Pulse	<90	90 - 99	100 - 150	151 - 170	170+	tranef	for to resus
1-2	RR	<20	20 - 24	25 - 35	36 - 50	50+	uansi	er to resus
	Temp	<35°	35 - 35.9°	36 - 38.4°	38.5 - 40°	40°+		
							*Signifi	cant PMH
	Pulse	<80	80 - 94	95 - 140	141 - 160	160+	include	s:
2-5	RR	<20	20 - 24	25 - 30	31 - 40	40+		
	Temp	<35°	35 - 35.9°	36 - 38.4°	38.5 - 40°	40°+	Ex-pre	emature
							Synar condit	ions
	Pulse	<70	70 - 79	80 - 120	121 - 150	150+	Cardia	ac problems
5-12	RR	<15	15 - 19	20 - 25	26 - 40	40+	Asthr	na l
	Temp	<35°	35 - 35.9°	36 - 38.4°	38.5 - 40°	40°+	Diabe	tes
			50.00		100 110		Long	term steroids
10.10	Pulse	<50	50 - 60	60 - 100	100 - 110	110+	 All oth 	er chronic
13-16		<12	12 - 14	15 - 20	20 - 25	25+	condit	ions
	Temp	<35°	35 - 35.9°	36 - 38.4°	38.5 - 40°	40°+		

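### The rule that fills missing AVPU from GCS puts GCS 9 in two levels, and it differs without explanation from the conversion used for PMEWS

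*SAP*

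**What the plan says.** Footnote a to the section 6.3 table of continuous characteristics has both scales analysed univariably, "however in multivariable analysis AVPU will be used and missing AVPU data will be imputed using GCE scores". The footnote writes GCE where GCS is meant, but its reference to 7.1.2 makes the sense clear.

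Section 7.1.2 repeats that, for the multivariable models, "GCS Total will be used to impute AVPU score where AVPU is not available". It then lists four bands: GCS 15 is A, 9 to 14 is V, 7 to 9 is P, and 3 to 6 is U. The AVPU row of the appendix (section 10) applies the GCS conversion first under both the assume-normal approach and multiple imputation.

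Section 8.3, for PMEWS when AVPU is missing and GCS is recorded, says to "impute the following AVPU scores using GCS: 0 if GCS=15, 1 if GCS=12-14; 2 if GCS=9-11 and 3 if GCS<9". On the PMEWS chart in that section, Alert scores 0, "Confused Agitated" scores 1, Voice scores 2, and Pain or unconscious scores 3. A note under the chart says that "confused/agitated will be defined based on GCS-V<4 or GCS total<15", or by a tick for confusion.

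Section 8.6.1, the WHO algorithm in children, counts consciousness as positive if "AVPU is P or U, or GCS<13".

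**The concern.** A pre-specified derivation has to return one value for each patient. The 7.1.2 rule does not do so at GCS 9, and every multivariable model that offers AVPU as a candidate is sent to it. Two programmers could both follow the SAP and build different datasets. If the bands are coded as successive overwrites in the listed order, GCS 9 ends as P; if they are coded as an if/else chain in that order, it ends as V. The planned comparison between multiple imputation and assume-normal imputation would not show this, because both use the same GCS conversion. The level chosen would pass into the coefficients, and from there into the integer weights of the triage score (the section on converting the model into a triage tool).

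Separately, 7.1.2 and 8.3 both describe themselves as filling AVPU from GCS, yet give different answers. A patient with the same GCS and no AVPU can therefore be coded one way in PMEWS and another way in the new models, which may be compared with PMEWS under section 6.5. The SAP does not say that this is intended.

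**Working it through.** No sample-size or power figure is involved. The check lists every GCS total from 3 to 15 (13 values) under each rule.

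**Inputs.** Bands from 7.1.2; points from the 8.3 conversion; chart values from the PMEWS table in 8.3 (Alert 0, Confused/Agitated 1, Voice 2, Pain or unconscious 3); child criterion from 8.6.1.

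| GCS | Level in 7.1.2 | That level in PMEWS chart points | Points given by 8.3 | 7.1.2 level ranked A=0, V=1, P=2, U=3 |
|---|---|---|---|---|
| 15 | A | 0 | 0 | 0 |
| 12–14 | V | 2 | 1 | 1 |
| 10–11 | V | 2 | 2 | 1 |
| 9 | V and P | 2 or 3 | 2 | 1 or 2 |
| 7–8 | P | 3 | 3 | 2 |
| 3–6 | U | 3 | 3 | 3 |

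**Step 1: is 7.1.2 well defined?** Twelve of the 13 totals fall in exactly one band. GCS 9 falls in two. No total is left out.

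**Step 2: does 8.3 agree with 7.1.2 when its scores are read as PMEWS points?** Compare columns 3 and 4. They agree at 15, 10–11 and 3–8. They differ at 12, 13 and 14 (2 against 1). GCS 9 cannot be compared until 7.1.2 is settled.

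**Step 3: does 8.3 agree if its 0 to 3 is read as A, V, P, U in order?** Compare columns 5 and 4. GCS 12–14 now agree, but 10–11 differ (V against P) and so do 7–8 (P against U). GCS 9 stays ambiguous. Neither reading reconciles the two sections.

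**Step 4: the child WHO criterion set beside 7.1.2.**

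| GCS | Positive by GCS below 13? | Level in 7.1.2 | Positive by AVPU P or U? |
|---|---|---|---|
| 13–15 | No | V (13–14), A (15) | No |
| 10–12 | Yes | V | No |
| 9 | Yes | V and P | Depends on the level |
| 3–8 | Yes | P or U | Yes |

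If the 7.1.2 equivalence is carried over, a child at GCS 10 to 12 meets this criterion when GCS is charted, but not when only AVPU V is charted. Section 8.6.1 does not itself invoke any conversion.

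**The case against.** The strongest reply is that only 7.1.2 governs the models. Footnote a, 7.1.2 and the appendix all point there; 8.3 fills only the PMEWS row. That row has a Confused/Agitated level that AVPU lacks, and 8.3 defines it to include GCS below 15, so one point for GCS 12 to 14 follows from the PMEWS chart. This stands. What is left between 7.1.2 and 8.3 is an unexplained difference, made worse because 8.3 calls its points AVPU scores.

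A reader might infer that coding GCS 12 to 14 as V is a second error in the model predictor, which dilutes the V coefficient by mixing confused patients with patients who respond only to voice. The SAP does not support that. A four-level scale must put these patients in A or V, and sections 8.2 and 8.4 pair GCS below 15 with AVPU other than A. Section 8.5 likewise scores confusion with Voice, Pain and Unresponsive. Nothing in the SAP says that confused patients would be charted as A.

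A reader might also want to recode purely verbal GCS loss as alert with confusion. That is unsound: eye 4, verbal 1, motor 6 totals 11 and has lost only verbal points (15 − 11 = 5 − 1 = 4), so a patient with no verbal response would become alert, although 7.1.2 and 8.3 both put GCS 11 at Voice.

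The grouping of GCS 13 to 15 in section 6.3 is not an error either. AVPU replaces GCS in the models, and GCS also appears in the univariable analysis as a continuous characteristic.

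Lastly, 8.6.1 describes an external tool, and its pairing of AVPU with GCS may be that tool's own. This cannot be settled from the SAP, so a check is all that can be asked.

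None of these replies resolves GCS 9.

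**Conclusion.** The 7.1.2 rule is wrong as written at one GCS total of 13, and it feeds the multivariable models. The difference between 7.1.2 and 8.3 is real under either reading of the 8.3 scores, but it is an inconsistency between two uses and leaves the model predictor determinate at GCS 12 to 14. The child WHO criterion does not line up with 7.1.2 at GCS 10 to 12, which may be legitimate.

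The effect of the conversion is confined to patients with AVPU missing and GCS recorded; recorded AVPU is used as it stands. The SAP gives no GCS distribution and no rate of missing AVPU, so neither the number of patients affected nor any change in a coefficient can be computed. Since the ambiguity concerns a single GCS value, the effect is probably small. The case for correction rests on the rule being indeterminate, with no claim of a material bias.

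**What to change.** 1. In 7.1.2, make the four bands mutually exclusive so that each GCS total from 3 to 15 has exactly one level. Which level GCS 9 takes is for the sponsor to decide.
2. In 8.3, either align the conversion with 7.1.2 or state that it assigns PMEWS points rather than AVPU levels, and that the difference from 7.1.2 is intended because the PMEWS chart has a Confused/Agitated level.
3. In 8.6.1, check the paired AVPU and GCS criteria against the cited WHO source and against 7.1.2. Then reconcile the passages, or state that the difference belongs to the tool.

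The cost is a few lines of SAP wording and of derivation code. No new data are needed.
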